13.4.6 Correlative Analyses

All analyses with respect to the correlative component of this study (Goal 1.2.5-1.2.9) are intended to be hypothesis-generating and descriptive in nature. Due to the exploratory nature of the correlative endpoints, we will not adjust for multiple comparisons for these analyses.

Descriptive statistics and simple scatterplots will form the basis of presentation of these data and any calculated changes from baseline. Single sample t-tests, Wilcoxon signed rank tests or McNamar's tests may be employed as appropriate. Data may be compared between success and failure groups using two sample t-tests or Wilcoxon rank sum tests. Correlations between these laboratory values and other outcome measures will be carried out by standard parametric and nonparametric correlation procedures (Pearson's and Spearman's coefficients).

13.5 Safety Analysis

13.5.1 A safety analysis will be performed after the first 6 patients have been accrued to the study on dose 0 (3 mg, orally days 1-21). If 2 or more of the first 6 patients experience a dose-limiting toxicity (DLT) as defined below, then 6 patients will be enrolled on dose -1 (2 mg, orally days 1-21). If 2 or more of the second 6 patients experience DLT, then the study will be terminated.

13.5.2 Toxicity will be measured per NCI-CTCAE version 4. DLT is defined as an adverse event possibly, probably, or definitely related to study treatment that meets one of the following:

- Any grade 4 drug-related non-hematological toxicity
- Any grade 3 drug-related non-hematological toxicity that does not resolve to < grade 3 within 3 days, with the following exceptions:
 - Grade 3 Bilirubin, AST, ALT, Alkaline phosphatase will be considered DLT only if it does not recover to <grade 3 within 7 days
- Myelosuppression: hypoplasia (bone marrow cellularity <10%) >50 days

13.6 Data Monitoring

The principal investigator(s) and the study statistician will review the study at least twice a year to identify accrual, adverse event, and any endpoint problems that might be developing. The accrual and safety data provided by Theradex for this trial will be reviewed and monitored by the Mayo Clinic Cancer Center (MCCC) Data Safety Monitoring Board (DSMB) at least twice a year, or more frequently as warranted.

13.6.1 Adverse Event Stopping Rule

The stopping rules specified below are based on the knowledge available at study development. We note that the Adverse Event Stopping Rule may be adjusted in the event of either (1) the study re-opening to accrual or (2) at any time during the conduct of the trial and in consideration of newly acquired information regarding the adverse event profile of the treatment(s) under investigation. The study team may choose to suspend accrual because of unexpected adverse event profiles that have not crossed the specified rule below.

Accrual will be temporarily suspended to this study if at any time we observe events considered at least possibly related to study treatment (i.e. an adverse event with attribute specified as “possible”, “probable”, or “definite”) that satisfy any of the following:

- If 3 or more out of the first 12 treated patients experience grade 4 non-hematological toxicities at least possibly related to treatment excluding fatigue, fever, infection, and lab abnormalities (hyper- or hypokalemia, hypocalcemia, hyperuricemia, hypophosphatemia) that resolve within 7 days without jeopardizing patient safety.
- If after the first 12 patients have been treated, 25% of patients experience grade 4 non-hematologic toxicities at least possibly related to treatment excluding fatigue, fever, infection, and lab abnormalities (hyper- or hypokalemia, hypocalcemia, hyperuricemia, hypophosphatemia) that resolve within 7 days without jeopardizing patient safety.

We note that we will review grade 4 and 5 adverse events deemed “unrelated” or “unlikely to be related”, to verify their attribution and to monitor the emergence of a previously unrecognized treatment-related adverse event.

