13.4.5 Adverse Events

All eligible patients that have initiated treatment will be considered evaluable for assessing adverse event rate(s). The maximum grade for each type of adverse event will be recorded for each patient, and frequency tables will be reviewed to determine patterns. Additionally, the relationship of the adverse event(s) to the study treatment will be taken into consideration.

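### Read literally, both accrual-suspension triggers in 13.6.1 count grade 4 but not grade 5, so a related death with no earlier qualifying event adds nothing to the count; the 13.5.2 DLT list is silent in the same way

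*Combined protocol and SAP*

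**What the plan says.** Section 13.6.1 holds the only rule that makes a temporary suspension of accrual mandatory. It has two triggers, both limited to events at least possibly related to treatment:

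- First 12 treated patients: "If 3 or more out of the first 12 treated patients experience grade 4 non-hematological toxicities at least possibly related to treatment".
- After the first 12: "25% of patients experience grade 4 non-hematologic toxicities at least possibly related to treatment".

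Both triggers exclude fatigue, fever, infection and a list of laboratory abnormalities, and the list ends with the clause "that resolve within 7 days without jeopardizing patient safety".

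The DLT definition in 13.5.2, which feeds the 2-of-6 rule in 13.5.1, has three items. They are "Any grade 4 drug-related non-hematological toxicity", grade 3 non-hematological toxicity that does not improve in the stated time, and marrow hypoplasia of more than 50 days.

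Within 13.5 and 13.6, grade 5 appears once, in the closing sentence of 13.6.1: "We note that we will review grade 4 and 5 adverse events deemed" unrelated or unlikely to be related. Elsewhere, 7.3.3 names grades 4 and 5 together, in its timeframe table and in its first footnote.

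Section 13.6.1 also provides discretion. The rule may be adjusted "at any time during the conduct of the trial and in consideration of newly acquired information", and "The study team may choose to suspend accrual because of unexpected adverse event profiles that have not crossed the specified rule below".

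**The concern.** A count of grade 4 events is not, in words, a count of grade 4 or worse. No section defines grade 4 as a floor, and the protocol writes grade 5 out where it wants it. Inside 13.6.1 the contrast is direct: grade 5 is named for events judged unrelated or unlikely to be related, and is missing from both triggers for related events. A death attributed as possible, probable or definite therefore falls outside the triggers and outside that closing review as well.

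The boundary also carries weight in the design. Section 13.1.2.7 cites the adverse event stopping rule, together with the small sample size, as a reason not to halt accrual while the first 11 patients become evaluable. A rule used in that way should clearly count the most severe related event.

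The exclusion list has a related gap. If the seven-day clause governs the whole list, a fatal infection is not excluded, because it did not resolve. If the clause governs only the laboratory abnormalities, infection is excluded without condition, and a fatal related infection would stay out of the count even after grade 5 is added. The text does not settle which reading applies.

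**Working it through.** **1. Literal counts.** The documents give no operating characteristics for the 3-of-12, 25% or 2-of-6 rules, so there is no figure of theirs to reproduce. The two triggers agree with each other (3/12 = 25%). Take a related death with no earlier qualifying event:

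| Situation | Count as written | Count if the death is included | Threshold |
|---|---|---|---|
| 3 such deaths in the first 12 | 0/12 | 3/12 | 3/12 |
| 2 grade 4 patients + 1 such death in the first 12 | 2/12 | 3/12 | 3/12 |
| 2 such deaths in the first 6 (DLT) | 0/6 | 2/6 | 2/6 |

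**2. Which deaths are affected.** A patient whose event passed through a counted grade 4 stage has experienced grade 4 and is counted. For the DLT list, so is a patient whose grade 3 toxicity failed to improve in time before death. The gap concerns only deaths with neither history.

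**3. Size.** Let g be the per-patient rate of counted grade 4 toxicity and d the per-patient rate of related death with no earlier qualifying event, treated as mutually exclusive. The rule as written uses p = g; if deaths count, p = g + d.

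- P(3-of-12 fires) = 1 − Σ(x = 0 to 2) C(12,x) pˣ(1−p)¹²⁻ˣ
- P(2-of-6 fires) = 1 − Σ(x = 0 to 1) C(6,x) pˣ(1−p)⁶⁻ˣ, leaving the other DLT items aside

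The documents give neither g nor d, so all values are assumptions. The lowest nonzero d is set near 1/142 = 0.7%: section 2.2.3 reports one death assessed as possibly related on INK128-001 and 142 treated patients there. That assumes the death falls within the 142 and had no earlier qualifying event. The values 3% and 5% have no anchor in the documents.

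| Rule | g | d = 0 (as written) | d = 0.7% | d = 3% | d = 5% |
|---|---|---|---|---|---|
| 3 of 12 | 10% | 0.111 | 0.129 | 0.198 | 0.264 |
| 3 of 12 | 20% | 0.442 | 0.466 | 0.545 | 0.609 |
| 2 of 6 | 10% | 0.114 | 0.128 | 0.178 | 0.224 |
| 2 of 6 | 20% | 0.345 | 0.362 | 0.418 | 0.466 |

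At d = 0.7%, the 3-of-12 probability rises by 0.1294 − 0.1109 = 0.019 (g = 10%) or 0.4663 − 0.4417 = 0.025 (g = 20%). The 2-of-6 probability rises by 0.1283 − 0.1143 = 0.014 or 0.3618 − 0.3446 = 0.017. At d = 5%, the 3-of-12 rises are 0.153 and 0.168.

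**The case against.** The strongest reply is that everyone would read grade 4 as grade 4 or worse, and that a related death would never go unnoticed. Much of this stands. The team may suspend accrual without a trigger (13.6.1). Adverse events enter any decision to terminate (13.1.4). The principal investigator and statistician have continuous data access, with calls every two months in the first year (12.1). The safety board reviews at least twice a year (13.6). Grade 5 events need 24-hour notification (7.3.3). Expected accrual is one evaluable patient per month (13.2.2), so a death would usually be known before the next enrolment. Section 13.1.2.7 also makes undue toxicity an exception to continued accrual and allows a pause if accrual is very rapid. These safeguards rest on judgement or reporting, however, and none puts a related death into the count.

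A reader might infer more than the documents support, in four ways:

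- *That deaths are ignored.* They are not, for the reasons just given.
- *That 13.6.1 is the only mandatory toxicity boundary.* It is the only mandatory accrual suspension, but 13.5.1 also requires action after 2 of 6 DLTs.
- *That a grade 4 event which turns fatal drops out, because under 13.4.5* "The maximum grade for each type of adverse event will be recorded for each patient". That section describes frequency tables. The triggers count patients who experience grade 4, and nothing makes the tables their source.
- *That one death would typically decide the 25% rule late on, for instance 6/26 = 23.1% against 7/26 = 26.9%.* The rule applies at any time. If six grade 4 patients are placed at random among 26 and observed in enrolment order, only 36,806 of 230,230 placements (16.0%) reach 6/26 without an earlier suspension. In the other 84% the rule has already fired.

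**Conclusion.** The point holds as a wording gap in the automatic boundary and should be fixed. Followed exactly, 13.6.1 returns 0/12 after three related deaths with no earlier qualifying event, which is surely not intended. The textual finding needs no assumed rate; it rests on no section defining grade 4 as a floor.

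The numerical effect is small unless such deaths are common: about 0.02 on the 3-of-12 probability at an assumed 0.7%, and up to about 0.17 only at an assumed 5%. The earlier possibly related death shows that the case is conceivable and establishes no rate for this trial. Section 2.2.3 adds that a later QT study found no clinically meaningful electrocardiographic effect. The exclusion-list ambiguity is real, but one of its two readings leaves no problem.

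**What to change.** 1. In both triggers of 13.6.1, write *grade 4 or 5*.
2. State in 13.6.1 whether the seven-day clause governs the whole exclusion list or only the laboratory abnormalities, so that a fatal related infection is not excluded by wording.
3. The sponsor should reconcile 13.5.2 with the grade 4 and 5 wording in the last sentence of 13.6.1 and in 7.3.3, and say whether related deaths count at the 2-of-6 look. No DLT or dose rule is proposed here.

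The cost is two words in each trigger, one clarifying phrase and one clarification in 13.5.2. Sample size, the efficacy design and data collection stay as they are, since 7.3.3 already requires attribution of deaths on study.

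### After a 13.5.1 de-escalation, the 13.6.1 suspension rule still counts the abandoned-dose cohort, which can mask a grade 4 rate above 25% at the dose in use

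*Combined protocol and SAP*

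**What the plan says.** Section 13.6.1 has two triggers for a temporary hold. The first is "If 3 or more out of the first 12 treated patients experience grade 4 non-hematological toxicities at least possibly related to treatment"; the second is "If after the first 12 patients have been treated, 25% of patients experience grade 4 non-hematologic toxicities". Both exclude fatigue, fever, infection and certain laboratory abnormalities that resolve within 7 days. They apply continuously: "Accrual will be temporarily suspended to this study if at any time we observe events". Neither names a dose level, and neither count restarts when the dose changes. Section 13.7.1 makes every treated patient evaluable for toxicity.

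Section 13.5.1 provides for a change of dose. "If 2 or more of the first 6 patients experience a dose-limiting toxicity (DLT) as defined below, then 6 patients will be enrolled" at dose -1 (2 mg, days 1-21). Then: "If 2 or more of the second 6 patients experience DLT, then the study will be terminated". So 0 or 1 DLT in six at dose -1 lets the study go on. Under 13.5.2 a related grade 4 non-hematological event is a DLT. So are a grade 3 event that does not resolve in time and prolonged marrow hypoplasia, neither of which 13.6.1 counts.

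For efficacy the plan does separate the doses: 13.1.2.3 keeps patients who are not at the safe dose out of the final decision rule. The safety rule has no counterpart.

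**The concern.** If 13.5.1 moves the trial to dose -1, the first 12 treated patients are six at the abandoned dose and six at the new one. The abandoned six then stay in the 25% denominator to the end. The rule no longer measures the toxicity of the dose being given to new patients.

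The direction of the distortion depends on how many of the abandoned six had an event that 13.6.1 counts. Call that number y. With y = 0 or 1, which is possible if the cohort was rejected for prolonged grade 3 events, the six mostly add event-free patients and the rule loses sensitivity. With y = 2 or more, the rule can call a hold at a point where 13.5.1 lets the study continue.

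The masking direction matters more, because accrual may continue at a dose whose observed rate is above the plan's own limit.

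**Working it through.** **Inputs from the documents.** 13.5.1: de-escalate at 2 or more of 6, and terminate at 2 or more of the second 6. 13.6.1: 3 of the first 12, then 25% (read as 25% or more). 13.2.1: 26 evaluable patients, 6 more after undue toxicity, and 3 spare.

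**The plan's own figures.** 13.6.1 gives no operating characteristics, so there is none to reproduce for this rule. The accrual total is 26 + 6 + 3 = 35, as stated, so the de-escalation branch is planned and budgeted. The 13.1.3 efficacy table also reproduces: exact two-stage binomial significance level 0.0865 (stated 0.09) and power 0.8516 at 30% (stated 0.85).

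**Assumptions.** The documents give no expected grade 4 rate, so the true rate p at dose -1 and the carried count y are varied. Events are independent.

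**Events needed to suspend.** With n patients at dose -1 (n > 6) and x counted events among them, the pooled rule needs (x + y)/(6 + n) of at least 25%. Counted at dose -1 alone, it needs x of at least 3 up to n = 12, then x/n of at least 25%.

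| n at dose -1 | Pooled, y = 0 | Pooled, y = 1 | Dose -1 alone |
|---|---|---|---|
| 12 | 5 | 4 | 3 |
| 18 | 6 | 5 | 5 |
| 26 | 8 | 7 | 7 |

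With y = 0, 4/12 = 33% is read as 4/18 = 22%, and 7/26 = 27% as 7/32 = 22%.

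**Event order.** Because the rule applies continuously, 4 of 12 does suspend if the fourth event falls by the 10th patient at dose -1: 4/16 = 25%. With at most one event in the first six, the possible orderings number C(6,4) + 6 × C(6,3) = 15 + 120 = 135. Those with all four events by patient 10 number C(4,4) + 6 × C(4,3) = 1 + 24 = 25. So 25 of 135 (19%) suspend and 110 do not.

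**Probability of suspension.** Exact patient-by-patient recursion: P(n, x) = (1 − p) P(n−1, x) + p P(n−1, x−1). Paths with 2 or more events in the first six are removed as terminated under 13.5.1, and paths that meet the trigger are removed as suspended. Results are divided by the probability of at most 1 event in the first six, which at p = 0.30 is 0.7^6 + 6 × 0.3 × 0.7^5 = 0.118 + 0.303 = 0.420.

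| y | p | By 12th at dose -1: pooled vs dose -1 alone | By 26th: pooled vs dose -1 alone |
|---|---|---|---|
| 0 | 0.30 | 8.2% vs 48.9% | 42.1% vs 74.4% |
| 1 | 0.30 | 30.8% vs 48.9% | 65.6% vs 74.4% |
| 0 | 0.20 | 2.1% vs 24.6% | 10.8% vs 39.0% |

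By the 26th patient with y = 0, the pairs are 24.3% vs 58.0% at p = 0.25 and 76.6% vs 93.4% at p = 0.40.

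**Opposite direction, y = 2.** One event in six at dose -1 makes 3 of 12. Given at most 1 of 6, its probability is 6p(1 − p)^5 divided by the probability of at most 1: 0.232/0.967 = 24% at p = 0.05 and 0.354/0.886 = 40% at p = 0.10. With y = 3 the trigger is met before anyone is treated at dose -1, while 13.5.1 directs that six be enrolled there.

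**How often the branch is reached.** P(2 or more of 6) = 11.4%, 34.5% and 58.0% at assumed DLT rates of 10%, 20% and 30%.

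**The case against.** **The masking scenario is uncommon.** If toxicity at the higher dose is at least that at the lower, then at a 30% rate the chance of no counted event in the abandoned six is at most 0.7^6 = 11.8%. Multiplied by the 42.0% chance of passing 13.5.1 at dose -1, the joint probability is at most 4.9%, before also requiring two DLTs that 13.6.1 does not count. Over all trials the gap is then at most 0.049 × (48.9 − 8.2) = 2.0 percentage points by the 12th patient and 0.049 × (74.4 − 42.1) = 1.6 points by the 26th. This stands: the large differences are conditional figures. The case of one carried event is additional, with a smaller gap.

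**Other safeguards exist.** The rule may be changed "at any time during the conduct of the trial and in consideration of newly acquired information regarding the adverse event profile", and "The study team may choose to suspend accrual because of unexpected adverse event profiles that have not crossed the specified rule below". The DSMB reviews the study at least twice a year (13.6), and investigator calls take place every two to three months (12.1). These soften the problem but leave the written count as it is. At one evaluable patient a month (13.2.2), about six patients could enter between scheduled DSMB reviews.

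**Pooling can be defended as a check on the agent.** A third related grade 4 event after a dose reduction is a reasonable occasion for a pause. This also stands. A reader might infer that 13.6.1 wrongly halts an acceptable dose or flatly contradicts 13.5.1. The documents do not support that: 13.6.1 calls a temporary hold, while 13.5.1 governs de-escalation and termination. Nor is the 24-40% to be set against a meaningful 0% for a dose-specific count. Once at most one event in six is assumed, three events at that dose are impossible by the sixth patient. What remains is that neither section says which governs.

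**The 20% row is not evidence of masking.** That rate is below the plan's 25% limit, so the extra suspensions there are a cost of dose-specific counting.

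**Conclusion.** The concern holds in a limited form. As written, 13.6.1 mixes an abandoned dose with the dose in use in a branch that the plan itself provides for. With no or one carried event, this makes the rule less sensitive to a rate above its own 25% limit. At an assumed true rate of 30%, suspension by the 12th patient at dose -1 falls from 49% to 8% (none carried) or 31% (one carried); by the 26th it falls from 74% to 42% or 66%.

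These figures require that de-escalation has occurred and that the dose -1 cohort has passed 13.5.1. They treat only counted grade 4 events as DLTs at dose -1, so they understate terminations under 13.5.1. Masking can begin only after the first six at dose -1, because two counted events among those six end the study.

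A reader might infer that 4 of 12 at dose -1 never suspends. That is too strong, since 25 of 135 orderings do. With two or more carried events the effect is an earlier temporary pause, and the defect there is the missing statement of precedence.

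**What to change.** Add to 13.6.1 that, after a 13.5.1 de-escalation, the existing triggers (3 of the first 12, then 25%) are also evaluated on patients who started at the dose in use, with that count beginning at the new dose. Starting dose is the workable definition, because sections 5 and 6 allow dose changes within a patient. Keep the pooled count for review, so that earlier grade 4 events are not lost. Reconcile 13.5.1 and 13.6.1 by stating which governs when one lets the study continue and the other suspends accrual. That choice is the sponsor's.

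The cost is about two sentences, with no new data and no change to any threshold or dose. The downside is more temporary holds when the true rate is just below 25%: at 20% with no carried events, 25% against 2% by the 12th patient at dose -1.

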13.7 Reporting and Exclusions

13.7.1 Evaluation of Toxicity

All patients will be evaluable for toxicity from the time of their first treatment with MLN0128 (TAK-228).

13.7.2 Evaluation of Response

All patients included in the study must be assessed for response to treatment, even if there are major protocol treatment deviations or if they are ineligible. Each patient will be assigned one of the following categories: 1) complete response, 2) partial response, 3) stable disease, 4) progressive disease, 5) early death from malignant disease, 6) early death from toxicity, 7) early death because of other cause, or 9) unknown (not assessable, insufficient data). [Note: By arbitrary convention, category 9 usually designates the “unknown” status of any type of data in a clinical database.]

All of the patients who met the eligibility criteria (with the possible exception of those who received no study medication) should be included in the main analysis of the response rate. Patients in response categories 4-9 should be considered to have a treatment failure (disease progression). Thus, an incorrect treatment schedule or drug administration does not result in exclusion from the analysis of the response rate. Precise definitions for categories 4-9 will be protocol specific.

All conclusions should be based on all eligible patients. Sub analyses may then be performed on the basis of a subset of patients, excluding those for whom major protocol deviations have been identified (e.g., early death due to other reasons, early discontinuation of treatment, major protocol violations, etc.). However, these sub analyses may not serve as the basis for drawing conclusions concerning treatment efficacy, and the reasons for excluding patients from the analysis should be clearly reported. The 95% confidence intervals should also be provided.

REFERENCES

1. Cancer Facts and Figures 2012. American Cancer Society. 2012.
4. Litzow MR. Novel therapeutic approaches for acute lymphoblastic leukemia. *Hematology/Oncology clinics of North America*. 2011;25:1303-17.
